6.9.5 Pharmacokinetic Population

All PK analyses will be performed using the PK population. All subjects who are enrolled and have a pre-dose sample and at least one post-dose analyzable sample will be included in the PK population.

6.10 Demographic and Other Baseline Characteristics

All demographic and baseline summaries will be done on the mITT, PP, safety, and PK populations.

Sex, race, and ethnicity will be summarized by counts and percentages. Age, height (cm), weight (kg), and BMI (kg/m²) will be summarized with descriptive statistics (n, mean, SD, median, min, and max).

EASI, BSA, ADIQ, Patient Oriented Eczema Measure (POEM), Dermatology Life Quality Index (DLQI), and Hospital Anxiety and Depression Scale (HADS) will be summarized with descriptive statistics (n, mean, SD, median, min, and max). IGA, Pruritus NRS, Sleep-loss NRS will be summarized by counts and percentages.

AD history, including number of years since onset, anatomical areas affected and prior AD treatments, will be summarized by counts and percentages. If only the year is known for start of AD the number of years since onset will be calculated by using January for month and “01” as day. If only the year and month are known for start of AD then onset will be calculated by using “01” as day.

Medical histories will be coded using the MedDRA dictionary and presented in a by-subject listing.

6.11 Prior and Concomitant Medications

Concomitant medications will be coded to preferred name and Anatomical Therapeutic Chemical (ATC) classification of ingredients using the WHO-DDE.

Counts and percentages will be provided to summarize the use of medications other than the study drug reported throughout the study. The number and percent of subjects who took other therapy will be shown by ATC level 2 term and preferred name. Medications which start prior to first dose will be considered prior medications. Ongoing medications and medications ending after the date of first dose will be considered concomitant medications. Medications that start on the date of first dose will be considered concomitant medications. Medications that end on the date of first dose will be considered prior medications. Medications which are both prior and concomitant will be included in both summaries. Incomplete or missing start and end dates which could be either prior to first dose or after first dose will be considered prior to first dose.

A by-subject listing of all prior and concomitant medications will be presented.

6.13.3 Sensitivity Efficacy Analysis

The sensitivity efficacy analysis will be presented on both the mITT and PP populations, except for sensitivity on observed data and sensitivity adjusting for subjects that use a rescue medication which will only be presented with the mITT population.

6.13.3.1 Sensitivity Using Non-Response Imputation

Sensitivity analyses will use NRI to impute missing values. The secondary endpoints of IGA and EASI75 at Week 16 will be analyzed using the same method as their corresponding secondary endpoint.

6.13.3.2 Repeated Measures Analyses on Observed Data

The second set of sensitivity analyses will be performed on observed data. The primary endpoint of percent change from baseline in EASI score at Week 16 will be analyzed with a repeated measures ANCOVA, with treatment, visit (Weeks 4, 8, 12, and 16), and treatment by visit interaction as factors, and a covariate of baseline EASI score.

The two dichotomized secondary endpoints of IGA and EASI75 at Week 16 will each be analyzed with a repeated measures logistic regression model (generalized estimating equations), with the dichotomized endpoint as the dependent variable and treatment, visit (Weeks 4, 8, 12, and 16), and treatment by visit interaction as factors.

6.13.3.3 Repeated Measures Analyses Adjusting for Rescue Medications

Sensitivity analyses adjusting for rescue medications will use NRI and LOCF to impute missing values (defined in Sections 6.1.7.1 and 6.1.7.2). The secondary endpoints of IGA and EASI75 at Week 16 will be analyzed using the same method as their corresponding repeated measures analyses on observed data.

6.14 Other Supportive Efficacy Analyses

Descriptive statistics will be presented for the following parameters by treatment group for both the mITT and PP populations:

- Descriptive statistics will be used to summarize EASI at each evaluation from Baseline through Week 24.
- Descriptive statistics will be used to summarize the absolute and percent change in EASI will be summarized at Weeks 4, 8, 12, 16, 20, and 24.
- Frequency and percent distributions of the dichotomized EASI score will be summarized at Weeks 4, 8, 12, 16, 20, and 24.
- Frequency and percent distributions of the IGA score will be summarized at each evaluation from Baseline through Week 24.
- Frequency and percent distributions of the dichotomized IGA scores will be summarized at Weeks 4, 8, 12, 16, 20, and 24.

- Descriptive statistics will be used to summarize Sleep-loss NRS will be summarized at each visit from Baseline through Week 16 and time points Days 2 through 7. Baseline (Day 1) – Day 7 are nominal study days from the date of first study drug injection (Day 1).
- Descriptive statistics will be used to summarize absolute and percent change in Sleep-loss NRS will be summarized at Weeks 2, 4, 6, 8, 10, 12, 14, and 16 and time points Days 2 through 7. Baseline (Day 1) – Day 7 are nominal study days from the date of first study drug injection (Day 1).
- Descriptive statistics will be used to summarize Pruritus NRS will be summarized at each visit from Baseline through Week 16 and time points Days 2 through 7. Baseline (Day 1) – Day 7 are nominal study days from the date of first study drug injection (Day 1).
- Descriptive statistics will be used to summarize absolute and percent change in Pruritus NRS will be summarized at Weeks 2, 4, 6, 8, 10, 12, 14, and 16 and time points Days 2 through 7. Baseline (Day 1) – Day 7 are nominal study days from the date of first study drug injection (Day 1).
- Frequency and percent distributions of the dichotomized Pruritus NRS will be summarized at Weeks 2, 4, 6, 8, 10, 12, 14, and 16 and time points Days 2 through 7. Baseline (Day 1) – Day 7 are nominal study days from the date of first study drug injection (Day 1).
- Descriptive statistics will be used to summarize BSA will be summarized at each evaluation from Baseline through Week 24.
- Descriptive statistics will be used to summarize absolute and percent change in BSA will be summarized at Weeks 4, 8, 12, 16, and 24.
- Descriptive statistics will be used to summarize ADIQ score will be summarized at each visit from Baseline through Week 16.
- Descriptive statistics will be used to summarize absolute and percent change in ADIQ score will be summarized at Weeks 2, 4, 6, 8, 10, 12, 14, and 16.
- Descriptive statistics will be used to summarize POEM score at Baseline, Week 16, and change from baseline at Week 16. The POEM score is calculated by summing the score of each question resulting in a maximum of 28 and a minimum of 0.

The scoring of each question is as follows:

No days	Scored 0
1-2 days	Scored 1
3-4 days	Scored 2
5-6 days	Scored 3

Every day Scored 4

The percentage of patients with POEM Score Change from Baseline ≥ 4 (Clinically Meaningful Difference) will be summarized for Week 16.

- Descriptive statistics will be used to summarize DLQI score at Baseline, Week 8, Week 16, and change from baseline at Weeks 8 and 16. Frequency and percent distributions of the dichotomized DLQI score to success (achieving total DLQI score of 0 or 1 – “No effect at all on patient's life”) will be summarized at Weeks 8 and 16. The DLQI score is calculated by summing the score of each question resulting in a maximum of 30 and a minimum of 0.

The scoring of each question is as follows:

Very much	Scored 3
A lot	Scored 2
A little	Scored 1
Not at all	Scored 0
Not relevant	Scored 0
Question 7, ‘prevented work or studying’	Scored 3

The percentage of patients with DLQI Score Change from Baseline ≥ 4 (Clinically Meaningful Difference) will be summarized for Weeks 8 and 16.

- Descriptive statistics will be used to summarize HADS depression and anxiety scores will be summarized at each visit from Baseline, Week 8, Week 16, and change from baseline at Weeks 8 and 16. The HADS depression and anxiety scores are calculated as the sum of each corresponding depression and anxiety question. Frequency and percent distributions of the HADS depression and anxiety scores at Weeks 8 and 16 using the following score ranges:

0-7 = Normal

8-10 = Borderline abnormal

11-21 = Abnormal

- Frequency and percent distributions of the Global Assessment of Change–AD will be summarized at Week 16.
- Descriptive statistics will be used to summarize the Global Assessment of Change–AD at Week 16.

6.15 Safety Evaluation

Safety analyses will be conducted on the safety population. No imputation will be made for missing safety data.

6.15.1 Extent of Exposure

The extent of exposure to study drug in each treatment group will be summarized by total number of days of exposure, total number of injections, number of missed injections, and number and percentage of subjects who are compliant. A subject will be considered compliant with the dosing regimen if the subject had at least 75% of the expected number of injections while enrolled in the study.

Missed injections are defined as the total number of missed or interrupted injections. If the subject discontinues the study early missed injections will also include any injections that should have been administered prior to the subject's date of treatment discontinuation.

Days of exposure = Date of last study injection – Date of first study injection + 1

The total number of injections taken is as follows:

The total number of recorded injections from the first injection until last injection.

The total number of injections expected is as follows:

- If completed/discontinued after at or after week 4 then:
 $8 + 2 * (\text{Last Study Visit Number Where Study Drug is Planned to be Administered} - 3)$.
- If discontinued prior to week 4 then:
 $4 * (\text{Last Study Visit Number Where Study Drug is Planned to be Administered} - 1)$.

The last study visit number where study drug is planned to be administered is as follows:

- If the date of treatment completion/discontinuation is on the same day as an actual subject visit or within window of a planned subject visit the last planned study visit is the visit prior. Otherwise, if the date of treatment completion/discontinuation is between visits windows, the visit prior to the study day of the date of treatment completion/discontinuation will be the last planned study visit.

Example 1: For a subject that completes treatment through Week 14 (Visit 9) the total number of expected injections would be $8 + 2 * (9 - 3) = 20$ injections.

Example 2: For a subject that discontinues between Week 8 (Visit 6) and Week 10 (Visit 7) the total number of expected injections would be $8 + 2 * (6 - 3) = 14$ injections.

Example 3: For a subject that discontinues between Week 2 (Visit 3) and Week 4 (Visit 4) and the date of discontinuation is prior to the minimum of the visit window for week 4 then the total number of expected injections would be $4 * (3 - 1) = 8$ injections.

Compliance will be calculated as a percentage as 100 times the total number of injections taken divided by the total number of injections expected.

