11.6 Exposure and Compliance

The extent of exposure to study drug in each treatment group will be summarized by total number of days of exposure, total number of applications, number of missed applications, and number and percentage of patients who are compliant. An application is considered the full set of injections (either 2 or 4 depending on visit) specified by the protocol.

A patient will be considered compliant with the dosing regimen if the patient received $\geq 75\%$ of the expected number of applications while enrolled in the study.

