6.9.4 Per-Protocol Population

All subjects in the safety population who complete the Week 16 evaluation without any significant protocol violations will be included in the PP population and analyzed according to the treatment group they received. The PP population will include subjects in the safety population who do not meet any of the following criteria:

- Violated the inclusion/exclusion criteria;
- Have taken any interfering concomitant medication;
- Did not attend the Week 16 visit;
- Missed more than 1 post-baseline study visit prior to Week 16;
- Did not receive at least 75% of the expected injections of study drug during participation in the study;
- Out of visit window at the Week 16 visit by ± 3 days;

Subjects who discontinue from the study due to an AE related to study treatment will be included in the PP population. Prior to breaking the blind, other additional criteria may be added to the list to accommodate for unforeseen events that occurred during the conduct of the trial that result in noteworthy study protocol violations.

All efficacy analyses will be performed on the PP population.

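### SAP 6.15.1 omits a dosed visit from expected injections when treatment stops on that visit day or within its window, which overstates compliance; separately, protocol and SAP count compliance in different units

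*SAP*

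**What the plan says.** SAP 6.15.1 gives two formulas for expected injections, both driven by the "Last Study Visit Number Where Study Drug is Planned to be Administered" (V below). For a patient who completes, or stops at or after Week 4, the count is 8 + 2 × (V − 3). For a patient who stops earlier it is 4 × (V − 1).

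V is chosen from the date on which treatment was completed or discontinued. When that date coincides with "an actual subject visit or within window of a planned subject visit the last planned study visit is the visit prior". A second branch covers stop dates that fall outside every window: "if the date of treatment completion/discontinuation is between visits windows, the visit prior to the study day of the date of treatment completion/discontinuation will be" taken as V.

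Compliance is "100 times the total number of injections taken divided by the total number of injections expected", and a patient is compliant if "the subject had at least 75% of the expected number of injections while enrolled in the study". There is no cap and no rule for a zero denominator. Three worked examples follow; the first reads "For a subject that completes treatment through Week 14 (Visit 9) the total number of expected injections would be" 20, and the other two give 14 and 8.

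SAP 6.9.4 uses the same threshold as a per-protocol exclusion: "Did not receive at least 75% of the expected injections of study drug during participation in the study".

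Protocol 11.6 also sets 75%, but counts applications: "An application is considered the full set of injections (either 2 or 4 depending on visit) specified by the protocol". SAP section 8 states that nothing in the planned analyses has changed.

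**The concern.** The numerator includes every recorded injection up to the last one. The denominator drops the visit at which treatment stopped, without asking whether the patient was dosed there. The two do not match whenever the stop date falls on a dosing day, or later in the same visit window.

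This is a foreseeable case. All injections are given in the clinic, and the events of special interest in protocol 9.1.7 include acute allergic reactions needing immediate treatment, so a patient may well stop on the day of a dose.

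At stake are the compliance and exposure table, agreement between programmers working from the same page, and, in limited circumstances, a per-protocol exclusion. The difference in unit is a second, independent reason why one patient can be compliant under one document and not under the other.

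**Working it through.** **Inputs.** Visit 2 (Baseline, Day 1) and Visit 3 (Week 2, Day 15) have 4 injections each. Visits 4 to 9 (Weeks 4 to 14; Days 29, 43, 57, 71, 85, 99) have 2 each (protocol 6.6). Visit 10 (Week 16, Day 113) has no dosing (Appendix 1, footnote c). Visit windows are ±3 days (protocol 7.3 and Appendix 1). I assume that these are the windows meant, and that dosing took place on target days.

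**1. The SAP's own figures.** With V = 9, 6 and 3:
- 8 + 2 × (9 − 3) = 20
- 8 + 2 × (6 − 3) = 14
- 4 × (3 − 1) = 8

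All three reproduce, and 20 equals the schedule total, 4 + 4 + 6 × 2. The formulas are sound. The fault lies in the text that selects V.

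**2. Stop date on a dosing day, patient fully dosed.** The rule sets V to the stop visit minus 1.

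| Stop visit | Taken = scheduled | Expected by the rule | Compliance |
|---|---|---|---|
| V2 (Day 1) | 4 | 4 × (1 − 1) = 0 | undefined |
| V3 | 8 | 4 × (2 − 1) = 4 | 200% |
| V4 | 10 | 8 + 2 × (3 − 3) = 8 | 125% |
| V5 | 12 | 10 | 120% |
| V6 | 14 | 12 | 116.7% |
| V7 | 16 | 14 | 114.3% |
| V8 | 18 | 16 | 112.5% |
| V9 | 20 | 18 | 111.1% |

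**3. All stop days from 1 to 113.** The rule undercounts on Day 1 and from the target day to three days after it for Visits 3 to 9: 1 + 7 × 4 = 29 days. On no day does it overcount.

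**4. Against Examples 2 and 3.**
- Example 3 (stop between Weeks 2 and 4, before the Week 4 window) covers Days 16 to 25 and gives 8. Days 16 to 18 are still in the Week 2 window, so the rule gives 4.
- Example 2 (stop between Weeks 8 and 10) covers Days 58 to 70 and gives 14. Days 58 to 60 are still in the Week 8 window, so the rule gives 12.
- If the contiguous windows of SAP 6.1.3 were meant instead, the Example 2 conflict widens to Days 58 to 64.

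**5. Crossing 75% through the rule.**
- No dose at Week 2, all other doses given, stop at Week 8 after dosing: 10/12 = 83.3% by the rule, 10/14 = 71.4% of scheduled.
- 14 injections with completion dated at the Week 14 dose: 14/18 = 77.8% by the rule, 14/20 = 70.0% of scheduled.

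**6. Crossing 75% through the unit.**
- No dose at Week 2 and at one later visit (six patterns): 6/8 = 75% of applications, compliant; 14/20 = 70% of injections, not compliant.
- The reverse also occurs. One of two injections missed at three to five visits gives 5/8 = 62.5% down to 3/8 = 37.5% of full applications, but 17/20 = 85% down to 15/20 = 75% of injections.

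**The case against.** **Stepping back one visit is often right.** Week 16 has no dosing, and Appendix 1 schedules no study drug at early termination. A stop dated at either visit is handled correctly. This stands: the error needs a stop date on a visit with dosing, or later in that visit's window.

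**Example 1 need not be contradicted.** A reader might infer that completers get 18 instead of 20. Protocol 4.1 runs treatment to Week 16, and 7.4 calls Day 113 the End-of-Treatment visit. A completion date there gives V = 9 and 20 injections, as Example 1 says. The figure of 18 needs completion to be dated at the last dose. The documents do not say so, though they do not define the date either.

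**Per-protocol membership is hardly touched.** A reader might infer that the rule moves patients both into and out of the set. It can only raise compliance. Early stoppers are also normally excluded in any case: protocol 10.3 sends them to early termination, and SAP 6.9.4 requires the Week 16 visit and at most one missed post-baseline visit. Those who leave the study for a treatment-related adverse event are included by a separate sentence. What remains is patients who attended visits without full dosing and still attended Week 16, or a completion date at Week 14.

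**The unit difference does not create two per-protocol sets.** The protocol's definition (11.2) contains no 75% cut. The only such cut is in SAP 6.9.4, in injections, consistent with SAP 6.15.1. The difference therefore affects the reported compliance percentage.

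**Conclusion.** The rule gives wrong numbers as written. When treatment stops on a dosed visit day or in the rest of its window (up to three days later, if dosing was on the target day), expected injections are too low by that visit's dose: 4 at Visits 2 and 3, 2 at Visits 4 to 9. The result is an undefined value on Day 1 and compliance of 200% down to 111% for fully dosed patients. The rule also conflicts with Examples 2 and 3.

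The consequence is minor. It falls mainly on a descriptive table, always in the direction of better compliance. The documents do not support a general distortion of the per-protocol set, and the mITT primary analysis does not use the quantity. The number of patients affected cannot be derived from the documents.

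The change of unit from applications to injections is real and undeclared, and can flip the compliance verdict in either direction.

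**What to change.** 1. Replace the rule that selects V. Expected injections are the sum of those scheduled (4 at Visits 2 and 3, 2 at Visits 4 to 9) over every dosing visit due on or before the stop date, including the stop visit if dosing was due or given there. Fully dosed patients then score 100% at every stop visit.
2. Define the date of treatment completion or discontinuation, in particular whether a completer's date is the Week 14 dose or the Week 16 visit.
3. Use one unit in protocol 11.6 and SAP 6.15.1 and 6.9.4, or declare the change in SAP section 8.

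A lighter repair, taking the later of the current rule's visit and the last visit with a recorded injection, is not enough. A patient who attends Visit 6 on Day 57, is not dosed although dosing was due, and stops on Day 59 would still have 12 expected where 14 were due. The two missed injections, which SAP 6.15.1 counts as missed, would be absent from the denominator.

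The cost is a few sentences in the SAP and a small programming change, with no effect on data collection or on the primary analysis.

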6.15.2 Anti-Drug Antibody (ADA) and NAb Data

ADA and NAb results will be summarized with descriptive statistics at Baseline, Weeks 2, 4, 16, and 24.

6.15.3 Pharmacokinetic Data

Plasma concentration data will be tabulated and summarized (n, n_{quant}, geometric mean, arithmetic mean, minimum, maximum, SD, and % coefficient of variation) by treatment group at Baseline, Weeks 2, 4, 8, 12, 16, and 24. Additionally the plasma concentrations will displayed graphically on linear and semi-logarithmic scales by treatment group and by subject.

6.15.4 Adverse Events

All AEs that occur during the study will be recorded and classified on the basis of MedDRA terminology. Treatment-emergent AEs (TEAEs) are defined as AEs with an onset on or after the date of the first study drug injection. If the start date for an adverse event is a partial date or missing and it cannot be determined as prior to or on/after first dose then the AE will be considered treatment-emergent. AE(s) noted prior to the first study drug administration that worsen after baseline will also be reported as AEs and included in the summaries.

Treatment-emergent AEs will be summarized by treatment group, the number of subjects reporting a TEAE, system organ class (SOC), preferred term (PT), severity, relationship to study drug (causality), and seriousness. When summarizing AEs by severity and relationship, each subject will be counted once within a SOC or a PT by using the event with the highest severity and greatest relationship within each classification.

No statistical inference between treatments will be performed on AE(s).

Listings will be presented for all AE(s) as well as for serious AE(s), and AE(s) leading to discontinuation from the study.

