11.7 Adverse Events

All AEs occurring during the study will be recorded and coded using the MedDRA dictionary. Treatment-emergent AEs (TEAEs) are defined as AEs with an onset date on or after the date of the first application. TEAEs will be summarized by treatment group, including the number of patients reporting an event, system organ class, preferred term, severity, relationship to study drug, and seriousness for the safety population. All serious AEs as well as AEs that led to study discontinuation will be listed by patient.

Three sets of AE tabulations are anticipated, one for the treatment period, one for the post-treatment (follow-up) period, and one for the combined treatment and post treatment period. The denominator used for the treatment period will correspond to the number of patients in the safety population. Data will also be corrected for exposure and reported per 100 patient-years.

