8. CHANGES IN THE PLANNED ANALYSES

There are no planned changes to the analyses.

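### SAP 6.15.4 omits, without declaring it, the period-specific AE tabulations and rates per 100 patient-years set out in Protocol 11.7, leaving one crude TEAE table in which about half the window follows the treatment period

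*SAP*

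**What the plan says.** Protocol 11.7 sets out two AE analyses beyond the basic summary. The first is a split by period: "Three sets of AE tabulations are anticipated, one for the treatment period, one for the post-treatment (follow-up) period, and one for the combined" treatment and post-treatment time. The second is a rate: "Data will also be corrected for exposure and reported per 100 patient-years".

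SAP 6.15.4 plans TEAE summaries by treatment group, system organ class, preferred term, severity, causality and seriousness, plus listings. It mentions neither a period split nor a patient-year rate. The only exposure measure in the SAP is in 6.15.1, which begins "Days of exposure = Date of last study injection" and subtracts the date of the first injection, plus one day. SAP 8 states "There are no planned changes to the analyses". The SAP change history records an edit to 6.15.4 about missing AE start dates, but no removal of these analyses.

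The TEAE definitions agree. The protocol has "Treatment-emergent AEs (TEAEs) are defined as AEs with an onset date on or after the date of the first application"; the SAP has "Treatment-emergent AEs (TEAEs) are defined as AEs with an onset on or after the date of the first study drug injection". Neither sets an end date. AEs are still reviewed and recorded at the Day 225 phone call (Protocol 7.7).

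**The concern.** With an open-ended TEAE definition, the protocol's period tables are what separate events arising during the treatment period from events arising in follow-up. Its patient-year rates are what allow for patients being observed for different lengths of time. The SAP keeps the open-ended definition and drops both.

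Followed as written, the SAP gives one percentage per arm and term over everything recorded from first injection to last contact. The documents show two ways in which observation time can become unequal:

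- Patients who need systemic AD therapy are discontinued from the study (Protocol 6.10). If that happened more often on placebo, which is an assumption, placebo patients would be observed for less time and a crude percentage would understate their AE frequency.
- The primary analysis runs once all patients have completed Week 16 and the final analysis after Week 32 (SAP 6.1). If AE tables are produced at the first of these without a period cut-off, they would mix patients with 16 weeks of observation and patients with up to 32.

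At stake is whether the safety tables can be read against placebo for the time on treatment. No test or error rate is affected.

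**Working it through.** **1. Stated durations and allocation.** The synopsis gives a treatment period of about 113 days and follow-up of about 111 days. From the visit days, 225 − 113 = 112, which agrees with 111. With 275 patients at 3:3:3:2, 275 × 3/11 = 75 per active arm and 275 × 2/11 = 50 on placebo, as stated.

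**2. Share of the AE window after the treatment period.**
- By visit days: (225 − 113)/225 = 112/225 = 49.8%.
- By stated durations: 111/(113 + 111) = 111/224 = 49.6%.
- After the last injection at Week 14 (Day 99): 126/225 = 56.0%.
- After the last active injection in the two every-4-week arms at Week 12 (Day 85): 140/225 = 62.2%.

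**3. Effect of merging the periods.** The documents give no AE rates, so these are assumptions. Take constant hazards, two periods of equal length, a treatment-period hazard ratio HR, and g = the fraction of the excess hazard that persists after the treatment period. Then

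combined rate ratio = (HR + 1 + g(HR − 1))/2.

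- HR = 2, g = 0: (2 + 1 + 0)/2 = 1.5.
- HR = 3, g = 0: (3 + 1 + 0)/2 = 2.0.
- HR = 2, g = 1: (2 + 1 + 1)/2 = 2.0, unchanged.

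On the crude-percentage scale that the SAP would report, let p0 be the 16-week placebo risk and HR = 2. The 16-week active risk is 1 − (1 − p0)². The 32-week risks are 1 − (1 − p0)² on placebo, and on active 1 − (1 − p0)³ if g = 0 or 1 − (1 − p0)⁴ if g = 1. For p0 = 10%: 19.0% vs 10.0% at 16 weeks; at 32 weeks 27.1% vs 19.0% (g = 0) or 34.4% vs 19.0% (g = 1).

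| p0 | 16-week risk ratio; difference | 32-week, g = 0 | 32-week, g = 1 |
|---|---|---|---|
| 2% | 1.98; 2.0 points | 1.49; 1.9 | 1.96; 3.8 |
| 10% | 1.90; 9.0 | 1.43; 8.1 | 1.81; 15.4 |
| 30% | 1.70; 21.0 | 1.29; 14.7 | 1.49; 25.0 |
| 50% | 1.50; 25.0 | 1.17; 12.5 | 1.25; 18.8 |

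If the excess ends at Week 16, ratios fall throughout, while the risk difference barely moves for rare events. If the excess persists in full, the rate ratio does not change, and the risk difference grows except for very common events.

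**4. What the protocol's rates would rest on.** With no dropout, an active arm has 75 × 113/365.25 = 23.2 patient-years in the treatment period and 75 × 112/365.25 = 23.0 in follow-up (46.2 combined). Placebo has 15.5 and 15.3 (30.8 combined).

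**5. Why time at risk needs its own definition.** For a completer, SAP 6.15.1 gives 99 days from first to last injection. Used as a denominator, it would inflate a treatment-period rate by 113/99 = 1.14 and a combined rate by 225/99 = 2.27.

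**The case against.** The strongest case is that little is lost. AE comparisons are descriptive, all AEs are listed, and onset is recorded (Protocol 9.1.5.1), so period tables can be derived later. SAP 6.7 summarises discontinuations at or before Week 16 by arm and 6.15.1 summarises exposure, so unequal dropout would be visible. The protocol only says that the tabulations are anticipated. A longer window may also capture more late events, and malignancy is among the AEs of special interest. All this is fair and limits the consequence. It does not remove the discrepancy: the patient-year sentence is unconditional, and the SAP says that nothing changed.

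A reader might infer more than the documents support:

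- **That the SAP widened the TEAE definition.** It did not; the protocol's definition is equally open-ended.
- **That half the window is off drug.** The documents as available give no half-life (the regimen rationale is redacted). PK is still sampled at Week 24, and contraception is required for 120 days after the last dose, which is Day 219 after a Day 99 injection. Only time after the treatment period can be claimed.
- **That differences between doses are diluted.** This depends on the excess risk ending with dosing, and the calculation above compares one active arm with placebo, not one dose with another.
- **That safety by dose is a stated objective.** The objectives name safety and efficacy versus placebo and, separately, dose-response without mention of safety.
- **That the SAP would compute inflated rates.** It plans no rates, and 6.15.1 serves the exposure summary. Among completers, the inflation factor would also be the same in every arm and leave ratios between arms unchanged.

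**Conclusion.** The concern holds as an undeclared departure of the SAP from Protocol 11.7: the period split and the patient-year rates are both missing. That conclusion comes from setting the texts side by side and needs no assumption. Nor does the size of the merged window beyond the visit schedule: 112 of 225 days, about half.

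The effect on comparisons between arms is conditional. An assumed treatment-period rate ratio of 2.0 becomes 1.5 if the excess stops at Week 16 and stays at 2.0 if it persists in full. These figures assume constant hazards, equal periods and no dropout. The documents do not say which case is nearer the truth, and the single planned table could not show it. The SAP should be corrected, but this is a matter of descriptive safety reporting and touches no efficacy conclusion.

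**What to change.** In SAP 6.15.4, restore the treatment-period, post-treatment and combined tabulations and add rates per 100 patient-years for each. Define time at risk by period:

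- treatment period and combined: from first dose to the end of that period, or last contact if earlier;
- post-treatment: from the start of that period to its end, or last contact if earlier.

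State that the first-to-last-injection days of 6.15.1 are not the denominator. Also state whether rates count all events or first events per patient, and which patients form the follow-up denominator, since Protocol 11.7 names only the one for the treatment period.

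If the sponsor intends to drop these analyses, SAP 8 should say so and give the reason.

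The cost is SAP wording and a few extra descriptive tables. AE onset is already collected, so no new data are needed.
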